#### **8.3.1.1. Reporting SAEs to Pfizer Safety**

All SAEs occurring in a participant during the active collection period are reported to Pfizer Safety on the CT SAE Report Form immediately and under no circumstance should this exceed 24 hours, as indicated in [Appendix 3](#). The investigator will submit any updated SAE data to the sponsor within 24 hours of it being available.

SAEs occurring in a participant after the active collection period has ended are reported to Pfizer Safety if the investigator becomes aware of them; at a minimum, all SAEs that the investigator believes have at least a reasonable possibility of being related to IP must be reported to Pfizer Safety.

#### **8.3.1.2. Recording Nonserious AEs and SAEs on the CRF**

All nonserious AEs and SAEs occurring in a participant during the active collection period, which begins after obtaining informed consent as described in [Section 8.3.1](#), will be recorded on the AE section of the CRF.

The investigator is to record on the CRF all directly observed and all spontaneously reported AEs and SAEs reported by the participant.

#### **8.3.2. Method of Detecting AEs and SAEs**

The method of recording, evaluating, and assessing causality of AEs and SAEs and the procedures for completing and transmitting SAE reports are provided in [Appendix 3](#).

Care will be taken not to introduce bias when detecting AEs and/or SAEs. Open-ended and nonleading verbal questioning of the participant is the preferred method to inquire about AE occurrences.

### **8.3.3. Follow-up of AEs and SAEs**

After the initial AE/SAE report, the investigator is required to proactively follow each participant at subsequent visits/contacts. For each event, the investigator must pursue and obtain adequate information until resolution, stabilization, the event is otherwise explained, or the participant is lost to follow-up (as defined in [Section 7.3](#)).

In general, follow-up information will include a description of the event in sufficient detail to allow for a complete medical assessment of the case and independent determination of possible causality. Any information relevant to the event, such as concomitant medications and illnesses, must be provided. In the case of a participant death, a summary of available autopsy findings must be submitted as soon as possible to Pfizer Safety.

Further information on follow-up procedures is given in [Appendix 3](#).

### **8.3.4. Regulatory Reporting Requirements for SAEs**

Prompt notification by the investigator to the sponsor of an SAE is essential so that legal obligations and ethical responsibilities towards the safety of participants and the safety of a study intervention under clinical investigation are met.

The sponsor has a legal responsibility to notify both the local regulatory authority and other regulatory agencies about the safety of a study intervention under clinical investigation. The sponsor will comply with country-specific regulatory requirements relating to safety reporting to the regulatory authority, institutional review boards (IRBs)/ethics committees (ECs), and investigators.

Investigator safety reports must be prepared for suspected unexpected serious adverse reactions (SUSARs) according to local regulatory requirements and sponsor policy and forwarded to investigators as necessary.

An investigator who receives an investigator safety report describing an SAE or other specific safety information (eg, summary or listing of SAEs) from the sponsor will review and then file it along with the investigator's brochure and will notify the IRB/EC, if appropriate according to local requirements.

### **8.3.5. Exposure During Pregnancy or Breastfeeding, and Occupational Exposure**

Exposure to the IP under study during pregnancy or breastfeeding and occupational exposure are reportable to Pfizer Safety within 24 hours of investigator awareness.

### **8.3.5.1. Exposure During Pregnancy**

Details of all pregnancies in female participants will be collected after the start of study intervention and until 28 calendar days after the last administration of IP.

If a pregnancy is reported, the investigator should inform the sponsor within 24 hours of learning of the pregnancy and should follow the procedures outlined in [Appendix 4](#).

Abnormal pregnancy outcomes (eg, spontaneous abortion, fetal death, stillbirth, congenital anomalies, ectopic pregnancy) are considered SAEs.

### **8.3.5.2. Exposure During Breastfeeding**

Scenarios of exposure during breastfeeding must be reported, irrespective of the presence of an associated SAE, to Pfizer Safety within 24 hours of the investigator's awareness, using the CT SAE Report Form. An exposure during breastfeeding report is not created when a Pfizer drug specifically approved for use in breastfeeding women (eg, vitamins) is administered in accord with authorized use. However, if the infant experiences an SAE associated with such a drug's administration, the SAE is reported together with the exposure during breastfeeding.

### **8.3.5.3. Occupational Exposure**

An occupational exposure occurs when, during the performance of job duties, a person (whether a healthcare professional or otherwise) gets in unplanned direct contact with the product, which may or may not lead to the occurrence of an AE.

An occupational exposure is reported to Pfizer Safety within 24 hours of the investigator's awareness, using the CT SAE Report Form, regardless of whether there is an associated SAE. Since the information does not pertain to a participant enrolled in the study, the information is not recorded on a CRF; however, a copy of the completed CT SAE Report Form is maintained in the investigator site file.

### **8.3.6. Medication Errors**

Medication errors may result from the administration or consumption of the IP by the wrong participant, or at the wrong time, or at the wrong dosage strength.

Exposures to the IP under study may occur in clinical trial settings, such as medication errors.

Safety Event	Recorded on the CRF	Reported on the CT SAE Report Form to Pfizer Safety Within 24 Hours of Awareness
Medication errors	All (regardless of whether associated with an AE)	Only if associated with an SAE

Medication errors include:

- Medication errors involving participant exposure to the IP;
- Potential medication errors or uses outside of what is foreseen in the protocol that do or do not involve the study participant.

Such medication errors occurring to a study participant are to be captured on the medication error page of the CRF, which is a specific version of the AE page.

In the event of a medication dosing error, the sponsor should be notified within 24 hours.

Whether or not the medication error is accompanied by an AE, as determined by the investigator, the medication error is recorded on the medication error page of the CRF and, if applicable, any associated AE(s), serious and nonserious, are recorded on an AE page of the CRF.

Medication errors should be reported to Pfizer Safety within 24 hours on a CT SAE Report Form **only when associated with an SAE**.

#### **8.4. Treatment of Overdose**

For this study, any dose of IP greater than 16 blinded tablets of PF-06882961 within a 24-hour time period  $\pm 2$  hours will be considered an overdose.

There is no specific antidote for overdose with PF-06882961. Treatment of overdose should consist of general supportive measures.

In the event of an overdose, the PF-06882961 should:

1. Contact the medical monitor within 24 hours.
2. Closely monitor the participant for any AEs/SAEs and laboratory abnormalities for at least 5 half-lives or 28 calendar days after the overdose of PF-06882961 (whichever is longer).
3. Obtain a blood sample for PK analysis within 2 days from the date of the last dose of study intervention if requested by the medical monitor (determined on a case-by-case basis).
4. Document the quantity of the excess dose as well as the duration of the overdose in the CRF.
5. Overdose is reportable to the Sponsor **only when associated with an SAE**. Refer to [Section 8.3.4](#) for regulatory reporting requirements.

Decisions regarding dose interruptions or modifications will be made by the investigator in consultation with the medical monitor based on the clinical evaluation of the participant.

### 8.5. Pharmacokinetics

In this study, blood samples (approximately 3 mL, each) to provide sufficient ***plasma*** for PK analysis will be collected into appropriately labeled tubes containing dipotassium edetic acid (ethylenediaminetetraacetic acid) - K2 EDTA, at times defined in the **SoA** – with collections occurring ***prior to dosing with IP*** on the given scheduled visit and between 2 and 6 hours post dose on 3 different visits: Visit 3, Visit 6 and Visit 9. The date/time of the blood collection and the date/time of the previous **2** doses of blinded IP prior to **each** of the blood collections related to PK (both pre- **and** post- dose samples) should be noted in a dosing diary (or similar) by the participants and captured in the CRF.

- The PK samples must be processed and shipped as indicated in the study-specific laboratory manual provided to the investigator site, prior to initiation of study, to maintain sample integrity:
  - Any deviations from the PK sample handling procedure (eg, sample collection and processing steps, interim storage or shipping conditions), including any actions taken, **must** be documented and reported to the sponsor. On a case-by-case basis, the sponsor may make a determination as to whether sample integrity has been compromised. Any deviation from the specified sample handling procedure resulting in compromised sample integrity will be considered a protocol deviation;
  - Any ***scheduled*** pre-dose collection [ie, trough concentration (Ctrough)] obtained post dose **or** any post dose samples **not** collected within the 2-6 hours post dose interval, will be captured as a protocol deviation even if results are deemed evaluable.
- As part of understanding the PK of the IP, samples may be used for metabolite identification and/or evaluation of the bioanalytical method, as well as for other internal exploratory purposes. These data may not be included in the clinical report.

Samples will be analyzed using a validated analytical method in compliance with Pfizer standard operating procedures.

### 8.6. Pharmacodynamics

PD parameters evaluated in this study include fasting plasma glucose, HbA1c and body weight and will be collected according to the **SoA**. The PD parameters of fasting plasma glucose and HbA1c will be assessed by the Central Laboratory as part of the clinical laboratory assessments (see **Appendix 2**), and body weight will be assessed as described in **Section 8.6.1**.

As part of understanding the PD of the IP, samples may be used for evaluation of the bioanalytical method, as well as for other internal exploratory purposes. These data will not be included in the clinical study report.

The PD samples must be processed and shipped as indicated in the instructions provided to the investigator site to maintain sample integrity. Any deviations from the PD sample handling procedure (eg, sample collection and processing steps, interim storage, or shipping conditions), including any actions taken, must be documented and reported to the sponsor. On a case-by-case basis, the sponsor may make a determination as to whether sample integrity has been compromised.

### **8.6.1. Body Weight**

Body weight will be measured in duplicate as indicated in the [SoA](#). The second weight measurement should be obtained at least 1-2 minutes apart from the first weight measurement.

Weight will be recorded using a calibrated scale (with the same scale used if possible for the duration of the study) reporting weight in either pounds (lb) or kilograms (kg), and accuracy to the nearest 0.2 lb (or 0.1 kg); ie, the device must be able to distinguish a difference between 150.4 lb (68.4 kg) versus 150.2 lb (68.3 kg). The scale must be placed on a stable, flat surface.

Weight measurement should be taken under the following conditions:

- Participant is in a fasted state (see [Section 5.3.1](#));
- After void of urine;
- After removal of shoes, bulky layers of clothing and jackets so that only light clothing remains;
- While remaining still during the measurement.

## **8.7. Genetics**

### **8.7.1. Specified Genetics**

Genetics (specified analyses) are not evaluated in this study.

### **8.7.2. Banked Biospecimens for Genetics**

An approximately 4 mL blood sample optimized for DNA isolation Prep D1 will be collected as local regulations and IRBs/ECs allow.

Banked biospecimens may be used for research related to drug response, T2DM and obesity. Genes and other analytes (eg, proteins, ribonucleic acid [RNA], nondrug metabolites) may be studied using the banked samples.

Unless prohibited by local regulations or IRB/EC decision, participants will be asked to indicate on the consent document whether they will allow their banked biospecimens to also be used to design and conduct research to gain a further understanding of other diseases and to advance science, including development of other medicines for patients. This component of the sampling banking is optional for participants; they may still participate in the study even if they do not agree to the additional research on their banked biospecimens. The optional additional research does not require the collection of any further samples.

See [Appendix 5](#) for information regarding genetic research. Details on processes for collection and shipment of these samples can be found in the laboratory manual.

## **8.8. Biomarkers**

Biomarkers are not evaluated in this study.

### **8.8.1. Specified Metabolomic Research**

Specified metabolomic research is not included in this study.

### **8.8.2. Banked Biospecimens for Biomarkers**

Serum (Prep B2.5) and plasma (Prep B1.5) samples of approximately 6-mL each will be collected according to the [SoA](#) and as local regulations and IRB/ECs allow.

Banked biospecimens may be used for research related to drug response, T2DM, and obesity. Genes and other analytes (eg, proteins, RNA, nondrug metabolites) may be studied using the banked samples.

Unless prohibited by local regulations or IRB/EC decision, participants will be asked to indicate on the consent document whether they will allow their banked samples to also be used to design and conduct research to gain a further understanding of other diseases and to advance science, including development of other medicines for patients. This component of the sampling banking is optional for participants; they may still participate in the study even if they do not agree to the additional research on their banked samples. The optional additional research does not require the collection of any further samples.

See [Appendix 5](#) for information regarding genetic research. Details on processes for collection and shipment of these samples can be found in the laboratory manual.

## **8.9. Health Economics**

Health economics/medical resource utilization and health economics parameters are not evaluated in this study.

## 9. STATISTICAL CONSIDERATIONS

Detailed methodology for summary and statistical analyses of the data collected in this study is outlined here and further detailed in a statistical analysis plan (SAP), which will be maintained by the sponsor. The SAP may modify what is outlined in the protocol where appropriate; however, any major modifications of the primary endpoint definitions or their analyses will also be reflected in a protocol amendment.

### 9.1. Estimands and Statistical Hypotheses

#### 9.1.1. Estimands

There are no estimands related to the primary objective and endpoint as outlined in [Section 3](#).

A summary of estimands is provided in the table below and described in detail thereafter:

Variable	Estimand	Population	Intercurrent Event	Population-level Summary	International Council for Harmonisation (ICH)-E9(R1) Strategy(ies)
Fasting Plasma Glucose (continuous endpoint)	1A	T2DM on background of metformin	Absence of glycemic rescue medication and discontinuation of study IP	Mean difference (PF-06882961 versus Placebo)	Hypothetical While on treatment
	1B	Non-diabetic with obesity	Discontinuation of study IP	Mean difference (PF-06882961 versus Placebo)	Hypothetical While on treatment
HbA1c (continuous endpoint)	2A	T2DM on background of metformin	Absence of glycemic rescue medication and discontinuation of study IP	Mean difference (PF-06882961 versus Placebo)	Hypothetical While on treatment
	2B	Non-diabetic with obesity	Discontinuation of study IP	Mean difference (PF-06882961 versus Placebo)	Hypothetical While on treatment
Body Weight (continuous endpoint)	3A	T2DM on background of metformin	Absence of glycemic rescue medication and discontinuation of study IP	Mean difference (PF-06882961 versus Placebo)	Hypothetical While on treatment
	3B	Non-diabetic with obesity	Discontinuation of study IP	Mean difference (PF-06882961 versus Placebo)	Hypothetical While on treatment

Estimand 1A will be the population average treatment effect on the change from baseline in FPG of PF-06882961 compared to placebo in participants with T2DM in the absence of glycemic rescue medication while on treatment and stable doses of background metformin. This reflects a combination of the ‘Hypothetical’ and ‘While on treatment’ strategies as outlined in the ICH-E9 (R1) draft guidance.

Measurements after initiation of glycemic rescue medication or discontinuation of IP will be censored and treated as missing data. Missing data due to censoring, study withdrawal or other reasons (eg, laboratory failure) will have data imputed based on a missing at random (MAR) assumption. Participants with inadequate compliance will have their fasting plasma glucose values used as-is in the analysis. The population-based treatment effect will be the difference in the mean change from baseline in each PF-06882961 arm compared to placebo. This estimand will be applied to the changes from baseline in FPG at Weeks 2, 4, 6, 8, 10 and 12.

Estimand 1B will be the population average treatment effect on the change from baseline in FPG of PF-06882961 compared to placebo in non-diabetic participants with obesity, while on treatment. This reflects a combination of the ‘Hypothetical’ and ‘While on treatment’ strategies as outlined in the ICH-E9 (R1) draft guidance.

Measurements after discontinuation of IP will be censored and treated as missing data. Missing data due to censoring, study withdrawal or other reasons (eg, laboratory failure) will have data imputed based on a missing at random (MAR) assumption. Participants with inadequate compliance will have their fasting plasma glucose values used as-is in the analysis. The population-based treatment effect will be the difference in the mean change from baseline in each PF-06882961 arm compared to placebo. This estimand will be applied to the changes from baseline in FPG at Weeks 2, 4, 6, 8, 10 and 12.

*Estimands related to other endpoints:*

Estimands 2A and 3A will utilize the same approach as Estimand 1A for the associated endpoints. Similarly, Estimands 2B and 3B will utilize the same approach as Estimand 1B for the associated endpoints.

Other exploratory/tertiary analyses may or may not be analyzed using these estimands and may be analyzed in a descriptive manner without reference to an estimand. Other estimands may be used for some of the primary and secondary endpoints as a means to examine the robustness of results, compare to available literature and/or be used for future study planning as needed. Details of these estimands and analyses will be presented in the SAP.

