### **6.5.1. Metformin**

All participants with T2DM are required to be taking metformin monotherapy prior to inclusion in this study as listed in [Section 5.1](#). Participants must have been taking a stable dose of metformin ( $\geq 500$  mg/day) for at least 60 days prior to the screening visit (Visit 1). Participants will continue taking their own metformin at the same total daily dose that was prescribed prior to study entry through the first follow-up visit (ie, Visit 10, Week 13-14), except in circumstances where a change in dose is deemed medically necessary. For study visit days, participants should be instructed to refrain from taking morning doses at home and to bring the metformin to the site for dosing at the same time as their blinded IP. For participants taking metformin more than once a day, the timing should be approximately the same on each day.

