### **6.5.3. Glycemic Rescue Medicine**

Participants with hyperglycemia as defined in [Section 8.2.4.3](#) should be offered glycemic rescue medication as an add on to their randomized treatment.

Glycemic rescue medication should be prescribed according to local label and obtained locally. The following glycemic rescue medications may be used: sulfonylureas, or sodium glucose co-transporter 2 (SGLT2) inhibitors. For participants who were taking a dose of metformin lower than the approved dose, increasing the metformin dose may be instituted as glycemic rescue medication, as long as the dose does not exceed the highest approved dose in the country of participation.

The following medication are NOT permitted as glycemic rescue medications: GLP-1R agonists, DPP-4 inhibitors, amylin analogues, thiazoledinediones (TZDs) or insulin.

The date of glycemic rescue medication administration as well as the name and dosage regimen of the glycemic rescue medication must be recorded on the CRF.

Participants receiving glycemic rescue medication should continue to follow all protocol specified visits and procedures according to the [SoA](#).

There is no rescue therapy to reverse the AEs observed with PF-06882961. Standard medical supportive care must be provided to manage the AEs, including administration of carbohydrates to treat HAEs (see [Section 8.2.4.2.1](#)).

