## 9.3. Populations for Analysis

For purposes of analysis, the following populations are defined:

Population	Description
Enrolled	All participants who sign the ICD.
Randomly assigned to IP	All participants randomly assigned to IP regardless of whether or not IP was administered.
Evaluable	All participants randomly assigned to IP and who take at least 1 dose of IP. Participants will be analyzed according to the randomized intervention.
Safety	All participants randomly assigned to IP and who take at least 1 dose of IP. Participants will be analyzed according to the product they actually received.

Defined Population for Analysis	Description
Estimand Set 1A (related to estimands 1A, 2A & 3A)	All evaluable participants with T2DM randomly assigned to IP and who take at least 1 dose of IP. For participants who discontinue IP and/or receive glycemic rescue medication, all subsequent values will be censored.
Estimand Set 1B (related to estimands 1B, 2B & 3B)	All evaluable non-diabetic participants with obesity randomly assigned to IP and who take at least 1 dose of IP. For participants who discontinue IP, all subsequent values will be censored.
PK Concentration Set	All participants randomly assigned to IP and who take at least 1 dose of PF-06882961 and in whom at least 1 concentration value is reported.

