## 10.8. Appendix 8: Prohibited Prior/Concomitant Medications

The following medications are prohibited until the first follow-up visit (ie, Visit 10, Week 13-14), unless stated otherwise. If a participant receives a prohibited medication, the investigator should contact the Sponsor Clinician or Sponsor Medical Monitor to determine if the participant may remain in the study.

Drug Classes and/or Drugs	Timeframe of Restriction Prior to Screening Visit
Thiazolidinediones (TZDs) such as pioglitazone and rosiglitazone.	90 days
Subcutaneously administered agents for glycemic control (eg, insulin, exenatide, liraglutide, dulaglutide, semaglutide, pramlintide). Note: Short-term (ie, $\leq$ 7 days) of insulin administration is permitted if participant is hospitalized.	90 days
Pharmacological agents with approved indication for weight loss such as liraglutide, orlistat and sibutramine.	90 days
Oral anti-diabetic medications, including:  Sulfonylureas such as acetohexamide, chlorpropamide, tolazamide, tolbutamine, glimepiride, glipizide, glyburide. Note: These may be used as glycemic rescue medications (See Section 6.5.3 ).  Meglitinide analogues such as repaglinide, nateglinide.  Dipeptidyl peptidase 4 inhibitors (DPP 4i) such as sitagliptin, saxagliptin, linagliptin, vildagliptin.  $\alpha$ glucosidase inhibitors such as acarbose, miglitol.  Sodium glucose cotransporter 2 (SGLT2) inhibitors such as canagliflozin, empagliflozin, dapagliflozin, ertugliflozin. Note: These may be used as glycemic rescue medications (See Section 6.5.3 ).  Anti-hyperglycemic medications, including bromocriptine and colesevelam.	60 days
Systemic glucocorticoids such as prednisone, dexamethasone, triamcinolone, budesonide, betamethasone. Note: As an exception, steroid-containing inhalers, nasal sprays and topical formulations are permitted. Note: Intercurrent treatment with systemic corticosteroids during participation in the study may be permitted if treatment does/will not exceed 7 days.	60 days
Immunosuppressants such as cyclosporine and tacrolimus.	60 days
Appetite or weight modifying medications, including nonprescription or herbals and medical grade marijuana.	60 days
Anti-psychotic medications such as olanzapine, risperidone.	60 days
Coumarin type anticoagulants or other anticoagulants (eg, dabigatran).	60 days
Anticonvulsants if prescribed for seizure disorder.	60 days

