**Estimands related to other endpoints:**

*Estimands 2A and 3A will utilize the same approach as Estimand 1A for the associated endpoints. Similarly, Estimand 3B will utilize the same approach as Estimand 1B (described in Section 2.1.3) for the associated endpoint.*

The above estimands related to T2DM participants on a background of metformin (1A, 2A and 3A) include the following 4 attributes:

- Population: Defined by the inclusion and exclusion criteria to reflect participants with T2DM who are on a background of metformin
- Variable: Change from baseline at Weeks 2, 4, 6, 8, 10 and 12 for FPG, HbA1c and Body Weight for Estimands 1A, 2A and 3A, respectively
- Intercurrent events: Measurements after initiation of glycemic rescue medication and/or discontinuation of study investigational product (IP) will be censored
- Population-level summary: Difference of variable means between PF-06882961 (each treatment group considered separately) and placebo

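### Estimands 1A–3A: only rescue and stopping IP trigger censoring, so non-rescue changes in glucose-lowering treatment stay in the analysis with no stated strategy

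*Protocol*

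**What the plan says.** **Target.** Protocol 9.1.1 describes Estimand 1A as the effect on FPG "in the absence of glycemic rescue medication while on treatment and stable doses of background metformin". Estimands 2A (HbA1c) and 3A (body weight) take the same approach. The strategy is a combination of hypothetical and while-on-treatment.

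**Rule.** Protocol 9.1.1: "Measurements after initiation of glycemic rescue medication or discontinuation of IP will be censored and treated as missing data". Protocol 9.3, Estimand Set 1A: "For participants who discontinue IP and/or receive glycemic rescue medication, all subsequent values will be censored". SAP 2.1.2: "Measurements after initiation of glycemic rescue medication and/or discontinuation of study investigational product (IP) will be censored". SAP Section 4 and SAP Appendix 1 carry the same two triggers. Missing values are then handled under MAR within the MMRM.

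**What counts as rescue.** Protocol 6.5.3 allows a sulfonylurea, an SGLT2 inhibitor or, where there is room, a higher metformin dose. It then states: "The following medication are NOT permitted as glycemic rescue medications: GLP-1R agonists, DPP-4 inhibitors, amylin analogues, thiazoledinediones (TZDs) or insulin".

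**What else may happen to background treatment.** Protocol 6.5.1 keeps metformin constant "except in circumstances where a change in dose is deemed medically necessary"; neither direction is excluded, and no link to the rescue criteria is made. Appendix 8 restricts injected glucose-lowering agents, but a note says that short-term use, up to 7 days, "of insulin administration is permitted if participant is hospitalized". If a prohibited drug is taken, "the investigator should contact the Sponsor Clinician or Sponsor Medical Monitor to determine if the participant may remain in the study". None of these passages says what happens to the participant's later FPG, HbA1c or weight values.

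**The concern.** The definition mentions stable metformin, but nothing in the censoring rule acts on it. A programmer who follows the SAP exactly would drop values after an SGLT2 inhibitor given as rescue, yet keep values after a DPP-4 inhibitor started in breach of Appendix 8, or after a metformin increase made below the rescue threshold. Pharmacologically these are the same kind of event, so treating them differently is hard to defend under a hypothetical strategy.

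The silence does not look like a stated choice. Protocol 9.1.1 addresses one other departure, poor compliance, and says that those values are kept. It also allows further estimands to test robustness, with details left to the SAP. SAP 6.2.1 and 6.2.2 give FPG and HbA1c a main analysis only. The supplementary analysis for body weight changes the scale to percent change, not the handling of these events.

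At stake is the meaning of the placebo-adjusted differences in T2DM. All five active arms are compared with one placebo group of about 15, so anything that moves the placebo mean moves all five contrasts together.

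**Working it through.** **1. Which events the rule reaches** (Protocol 6.5.1, 6.5.3 and Appendix 8 set against 9.1.1 and 9.3, and SAP 2.1.2, Section 4 and Appendix 1):

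| Event in a T2DM participant | Later values censored? |
|---|---|
| Sulfonylurea or SGLT2 inhibitor given as rescue | Yes |
| Metformin increase given as rescue | Yes |
| Prohibited drug leading to IP stop or withdrawal | Yes, or missing |
| Sulfonylurea, SGLT2 inhibitor or metformin increase without the rescue criteria met | Not defined; depends on coding |
| Metformin reduction | No |
| Hospital insulin up to 7 days | No; insulin is expressly not rescue |
| Other prohibited glucose-lowering drug, participant stays on IP | No |

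The gap is the last four rows.

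**2. Could these events occur?** Entry HbA1c may be as high as 10.5% (Protocol 5.1.2). Rescue needs a fasting glucose of at least 270 mg/dL, repeated and then confirmed centrally (8.2.4.3). Sites do not see central FPG or HbA1c below that level (Appendix 2), but they review home readings taken at least three times a week (8.2.4.1). A change of treatment below the threshold is therefore possible. The documents give no frequency.

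**3. The plan's own numbers** (Protocol 9.2). T2DM: 5 × 20 + 15 = 115. Obesity: 20 + 5 = 25. Total 140; 140 × (1 − 0.25) = 105 completers, as stated. No power, SD or target effect is given, so there is no power figure to reproduce. Placebo T2DM completers: 15 × 0.75 = 11.25, about 11.

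**4. Size, on stated assumptions.** If k of n participants in an arm keep values displaced by e, the arm mean moves by about e × k/n. The values of k and e below are assumptions.

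Placebo, added glucose lowering, n = 15:
- Share affected: 1/15 = 6.7% to 3/15 = 20%.
- HbA1c, e = 0.3 to 1.0 points: 0.3 × 1/15 = 0.02 to 1.0 × 3/15 = 0.20 points.
- FPG, e = 15 to 50 mg/dL: 15 × 1/15 = 1.0 to 50 × 3/15 = 10 mg/dL.

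Placebo with n = 11 completers:
- HbA1c: 0.3 × 1/11 = 0.03 to 1.0 × 3/11 = 0.27 points.
- FPG: 15 × 1/11 = 1.4 to 50 × 3/11 = 13.6 mg/dL.

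One active arm, n = 20, metformin reduced, same assumed e for HbA1c: 0.3 × 1/20 = 0.015 to 1.0 × 3/20 = 0.15 points.

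**5. Direction.** Added glucose lowering on placebo shrinks the contrast. A metformin reduction in an active arm also shrinks it. A metformin reduction on placebo, or added treatment in an active arm, enlarges it.

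**The case against.** The strongest reply is that stable metformin describes the population and is not a condition to be enforced after randomization. The objectives tables (Protocol Section 3, SAP 2.1) attach it to the participants, SAP 2.1.2 lists background metformin under Population, and the two intercurrent events tabulated in Protocol 9.1.1 are exactly the two that are censored. On this reading the plan leaves other medication changes to an implicit treatment-policy approach. That stands as a possible reading, so a reader should not conclude that the analysis plainly fails its estimand. It does not remove the point: 9.1.1 places the stability wording alongside being on treatment, and an implicit strategy is still an unstated one.

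Protocol 6.5 and 6.5.2 discourage metformin changes and bar other glycemic drugs unless rescue criteria are met. Sites are largely blinded to central results. SAP 6.5.2 and 6.5.4 report important deviations and concomitant drugs. The events may therefore be rare, and many would be visible. That limits the importance of the point, but it supplies no analysis rule.

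A reader might infer from SAP Appendix 3, whose PD dataset carries only a rescue flag, that other events would be missed in programming. That does not follow: the dataset is meant for exploration and model checking, and it has no IP-discontinuation flag either, although that is an explicit trigger.

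Finally, censoring everything after any metformin change or a few days of insulin would discard on-treatment data in arms of 15 to 20. It could be informative under MAR if metformin cuts cluster in participants with GI intolerance. This objection stands, and the fix below is limited accordingly.

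**Conclusion.** The point holds in a bounded form. Both documents censor only at glycemic rescue or IP discontinuation. Metformin changes not given as rescue, permitted hospital insulin, and prohibited glucose-lowering drugs in participants who stay on IP therefore remain in the FPG, HbA1c and weight analyses, and no strategy is stated for them.

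Two stronger readings are not supported. One is that all metformin changes and all added drugs stay in: Protocol 6.5.3 makes a metformin increase, a sulfonylurea or an SGLT2 inhibitor a censoring event when given as rescue. The other is that the differences are biased toward zero: that is one plausible pattern, but the opposite pattern cannot be excluded, and the documents give neither rates nor effect sizes.

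The illustrative placebo shifts of 0.02 to 0.20 HbA1c points and 1 to 10 mg/dL FPG rest wholly on an assumed one to three affected participants out of 15 and assumed displacements. With no SD or target effect in the plan, they cannot be shown to change a conclusion. These are secondary endpoints, without multiplicity control, in a study sized empirically for tolerability. The change is worth making because it is cheap and settles what is being estimated.

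**What to change.** This is a change to the analysis only; no treatment rule is touched.

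1. **Main rule.** In SAP 2.1.2, Section 4 and Appendix 1, with Protocol 9.1.1 and 9.3 aligned, define the rescue trigger for Estimand Set 1A as the start of any sustained glucose-lowering medication other than IP, or any metformin increase above the baseline total daily dose, whether or not the rescue criteria were formally met. Define sustained; the simplest definition is any use other than the hospital insulin course of up to 7 days that Appendix 8 allows. IP discontinuation remains the other trigger.
2. **Sensitivity analysis.** Apply rule 1 and also censor after a metformin reduction, exclude values during and shortly after short-term hospital insulin (with the window stated in advance), and, for 3A and 3B, censor after first use of a prohibited weight-affecting drug.
3. **Further sensitivity analysis.** Report the plan's present two-trigger rule, so that the effect of the wider trigger can be seen.
4. **Data.** Derive a dated background-change flag. Protocol 6.5 already requires dose changes in the CRF and start and stop dates for concomitant treatments, and SAP 6.5.1 already summarises baseline metformin daily dose.

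The work is a few lines of text, one derived variable and two extra model runs. Protocol Section 9 and SAP Section 2 let the SAP modify the plan, and require an amendment only for major changes to the primary endpoint or its analysis, so the SAP can carry this before unblinding. The statistical cost is a few more censored values and slightly wider intervals, with somewhat more reliance on MAR. Keeping metformin reductions and brief hospital insulin out of the main rule limits that cost.
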